3. STUDY DRUG ACCESS

To maintain dosing continuity during the COVID-19 pandemic, study drug may be shipped from the sites to patients using couriered tracking services, when a patient is not able or willing to travel to the study site. Drug will not be shipped directly from the Sponsor to patients. Stability information for study drug shipments is contained in the “Guidance for Direct-to-Patient Shipping of RTA-402 Drug Product Capsules during the Coronavirus (COVID-19) Pandemic” (Attachment 1). For shipments anticipated to exceed a 48-hour transit time, sites will be supplied with temperature monitors upon request. When a shipment exceeds this transit time, the Sponsor should be notified immediately via the COVID-19 Investigational Product Temperature Excursion Form. The Sponsor will assess whether the product is fit for use. During this assessment period, the patient should be informed to not take the Study drug until further notice from the site. Study drug dispensation should be recorded in the appropriate drug accountability logs and all study drug receipts of delivery should be filed in the Investigative Site File. patient

4. STUDY VISITS

If sites foresee upcoming closures or other issues impacting the patient’s ability to come in for frequent visits (first 8 weeks), consider postponing the patient’s enrollment. The Day 1 visit of EAGLE will not be required to occur on the same day as the end-of-study visit of prior qualifying study.

For continued patient safety oversight, patients should continue with protocol-specified visits. Where inadvisable for the patient to be seen for an in-person, in-clinic visit or if a patient is unwillingly to come to the clinic, alternate visit completion methods should be considered, such as by phone, telemedicine, home health visits and/or local laboratory monitoring of safety labs.

Visits conducted over the phone (or via telemedicine, if available), at a minimum should include the following assessments:

- Adverse-event assessment
- Prior and concomitant medication assessment

In-home visits at a minimum should include the following assessments:

- Safety labs (may also be done by local laboratories)
 - Clinical chemistry (including eGFR)
 - BNP and NT-proBNP
 - Hematology
 - Urine collection for ACR
 - Urine pregnancy test for WOCBP
- Vital signs
- Weight at home
- Adverse event assessment

- Prior and concomitant medication assessment

5. DOSE MANAGEMENT

5.1. Dose De-escalation and Interruption for Missed Safety and Laboratory Assessments

If no scheduled in-clinic visit is completed and remote assessments/laboratory samples cannot be collected within the protocol allowed time window for that visit, the IP dose must be de-escalated to the previous dose within 6 days of the protocol visit window. For patients on 5 mg, the lowest dose, that dose may be maintained, and no de-escalation is required. All efforts should then be made to collect laboratory samples. However, if laboratory samples cannot be collected within 14 days from the date of dose de-escalation (for visits through Week 12) and within 28 days (for visits beyond Week 12), IP must be temporarily interrupted until safety lab values can be evaluated and it is deemed appropriate to restart. Appendix 1 Section 5.2 describes the procedure for resuming and dose-escalating IP following drug interruption.

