7.3.1. Dose Escalation

Adult patients (≥ 18 years of age) receiving bardoxolone methyl will start with once-daily dosing at 5 mg and will dose-escalate to 10 mg at Week 2, to 20 mg at Week 4, and then to 30 mg at Week 6 (only if eligibility ACR > 300 mg/g) unless contraindicated clinically and approved by the medical monitor. Patients from the CARDINAL study under the age of 18 at the time of consent for participation in the EAGLE study will start dosing at 5 mg every other day during the first week (from Day 1 through the Week 1 visit) and begin once-daily dosing with 5 mg during the second week of the study (following the Week 1 visit through the Week 2 visit), and then continue with once-daily dosing following the same aforementioned dose-titration scheme based on eligibility ACR at Weeks 2, 4, and 6. Patients from the FALCON study under the age of 18 at the time of consent for participation in the EAGLE study will follow the adult dose titration schedule. Dose escalation may proceed slowly if the patient experiences early elevation in ALT/AST over ULN eg, at Week 2 (See Section 9.1.2). The dosing objective is to titrate patients to the maximum dose determined by eligibility ACR and maintain the maximum dose after initial dose-titration. The investigator should discuss any reason for not dose-escalating at Weeks 2, 4, or 6 with the medical monitor.

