7.3.2. Dose De-Escalation and Re-Escalation

The investigator may choose to decrease the patient's dose to the prior dose (eg, 20 mg to 10 mg, or 10 mg to 5 mg), if clinically indicated. Dose de-escalation may occur more than once, but the minimum dose permitted is 5 mg. Reasons for dose de-escalation should be discussed with the medical monitor prior to changing the dose and must be documented. After dose de-escalation, patients must return for an unscheduled, in-clinic visit within 4 weeks (± 3 days) to perform the assessments detailed in Section 9.6.

If a patient's dose has been reduced, dose re-escalation back to a higher dose is permitted to meet the dosing objective. However, patients who dose re-escalate must have a telephone call 1 week (± 2 days) after dose re-escalation and an unscheduled, in-clinic visit 2 weeks (± 3 days) after dose re-escalation to perform the assessments detailed in Section 9.6.

Patients who had a delayed initial dose-escalation should also have a telephone call 1 week (± 2 days) after each dose escalation and an in-clinic visit 2 weeks (± 3 days) after dose escalation to perform the assessments detailed in Section 9.6. If these timepoints no longer coincide with scheduled study visits, unscheduled phone calls and in-clinic visits should occur. These do not replace the regularly scheduled study visits; they should be performed as well.

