^b After the Week 24 visit, subjects will continue to be assessed in person every 24 weeks until the study ends. The End -of- Study visit should occur within 30 days after bardoxolone methyl becomes available to the subject through commercial channels. For additional details, see Section 7.4. Subjects who will be discontinued from the study prior to commercial availability of bardoxolone methyl must also complete all End-of-Study assessments as soon as possible (if possible, within 30 days of discontinuation).

^c On Day 1, all procedures should be performed before study drug administration. AE assessment on Day 1 should be performed following study drug administration. If the Day 1 visit for EAGLE is the same as the end-of-study visit for CARDINAL (all versions) or FALCON (protocol version 5 and older), the laboratory assessments required for both visits should only be completed once.

If the Day 1 visit for EAGLE is the same as the end-of-study visit for FALCON (protocol version 6 and newer), the lab assessments required for both visits should be completed for each study individually.

^d Demographics are to be performed on the earliest study visit, whether it be Day 1 or a Screening visit, if necessary.

^e Assessment should include a complete physical examination as described in Section 9.9.7.

^f A serum pregnancy test will be performed at any point in time if a pregnancy is suspected. All other pregnancy assessments will be urine pregnancy tests. Additional pregnancy assessments will be performed more frequently if required by local law or requested by local health authorities or IRBs/IECs.

^g eGFR will not be calculated by the central lab.

^h Urine albumin to creatinine ratio will be measured by first morning void spot urine collection. Appropriate containers for the collection will be provided to the subject at the visit prior to collection.

ⁱ Adolescent patients from the FALCON (402-C-1808) ($12 \leq \text{age} < 18$ years at consent) will be assessed by Tanner staging at all specified timepoints.

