9.1.1. Management of Fluid Status

Specific risk mitigation procedures will be employed to reduce the potential for bardoxolone methyl-induced fluid overload. Laboratory data will be used to monitor fluid status after enrollment. Patients who experience a BNP > 100 pg/mL that represents a doubling (or more) of BNP levels from Day 1 should have an unscheduled telephone contact immediately. If fluid retention is suspected, the patient should be instructed to stop taking study medication immediately and be medically evaluated by the investigator or a local physician within 1 to 2 days.

Additionally, after enrollment and starting study treatment, patients will be closely monitored for rapid weight gain suggestive of fluid overload. Patients will be given a Sponsor-provided scale to use at home to collect and record their weights daily during the first 8 weeks of the treatment period and weekly thereafter. In the event the Sponsor-provided scale is temporarily unavailable (eg, subject is traveling, replacement scale has not arrived to subject, etc.), subjects may use any available scale. Use of a scale other than the Sponsor-provided scale should be documented in the subject diary. During the first 8 weeks, patients who experience a five-pound (2.3 kg) or greater increase in weight in one week or 3 pounds (1.4 kg) in one day should have an unscheduled telephone contact immediately. Whether prompted by BNP elevations, sudden weight gain, or by the presence of clinical signs and symptoms the patient must be instructed to stop taking their study medication immediately and be medically evaluated by the investigator or a local physician within 1 to 2 days.

Investigators are encouraged to start or increase doses of diuretics (thiazides, loop diuretics) early after recognition of edema. This can be done concurrently with temporary drug interruption and re-initiation. Patients may not restart their study medication until the investigator has completed and documented an assessment of fluid overload.

After Week 8, patients who experience a five-pound (2.3 kg) or greater increase in weight in one week will be instructed to return to the clinic for an unscheduled physical examination and laboratory assessment by the investigator. Study medication should not be interrupted until the investigator has completed and documented an assessment of fluid overload.

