9.1.2. Management of Elevated Aminotransferase Levels (ALT and/or AST)

For all patients enrolled, nearly all instances of elevated aminotransferases due to bardoxolone methyl treatment are expected to be asymptomatic. Some patients may experience more rapid increases in ALT/AST values than others during the dose titration period. Investigators may consider extending the time between each dose increase to manage ALT/AST elevations.

If a patient's transaminases are elevated, follow the instructions outlined in Table 6.

Table 6: Management of Elevated Aminotransferase Levels (ALT and/or AST)

ALT and/or AST Level(s)	Dose Interruption (yes/no)	Procedure
> 8X ULN	Yes	Interrupt study drug temporarily Contact the medical monitor
> 5X ULN for more than 2 weeks		The study drug may be restarted with Sponsor approval after all the following criteria are met: 
 • Ultrasound or MRI of the hepatobiliary tree*; • ALT and AST returned to \leq ULN; • TBL is within normal range; • Other relevant labs (eg, albumin, INR, PT) are within normal range; • No clinical signs or symptoms of liver injury are present.
> 3X ULN with the appearance of fatigue, nausea, vomiting, right upper quadrant pain or tenderness, fever, rash, and/or eosinophilia		
> 3X ULN and (TBL > 2X ULN or INR > 1.5)		
> 3X ULN	No	Check transaminase levels (as well as TBL, GGT, alkaline phosphatase [ALP], and International Normalized Ratio [INR]) within 48 to 72 hours Continue testing for ALT/AST every 72 to 96 hours until transaminase levels are below 3X the ULN for at least 1 week
Abbreviations: ALP=alkaline phosphatase; ALT=alanine aminotransferase; AST=aspartate aminotransferase; GGT=gamma-glutamyl transpeptidase; INR=international normalized ratio; MRI=magnetic resonance imaging; PT=prothrombin time; TBL=total bilirubin; ULN=upper limit of normal		

Patients restarting study drug after meeting these interruption criteria should start at the 5 mg dose level and dose titrate according to Section 7.3.2.

The hepatobiliary tree must be assessed by ultrasound or magnetic resonance imaging (MRI) for patients who meet temporary interruption criteria. Based on imaging results, if patient additional tests/studies are warranted, this should be discussed with the medical monitor.

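### The missed-lab interruption limit in Appendix 1 is counted from a dose de-escalation that patients on 5 mg never have

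*Protocol*

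**What the plan says.** Appendix 1, Section 5.1 is a two-step rule, triggered when no clinic visit takes place and remote assessments or samples cannot be obtained inside the visit window.

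- **Step 1, reduce.** The dose goes down one level within 6 days of the visit window. The lowest dose is exempt: "For patients on 5 mg, the lowest dose, that dose may be maintained, and no de-escalation is required". This agrees with Section 7.3.2: "Dose de-escalation may occur more than once, but the minimum dose permitted is 5 mg".
- **Step 2, interrupt.** Sites are to make every effort to obtain the samples. For early visits the limit applies "if laboratory samples cannot be collected within 14 days from the date of dose de-escalation (for visits through Week 12". For later visits the sentence goes on: "and within 28 days (for visits beyond Week 12), IP must be temporarily interrupted until safety lab values can be evaluated".

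The 28-day part names no start of its own.

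Several groups can be on 5 mg when a visit is missed. Under Section 7.3.1 adults "will start with once-daily dosing at 5 mg and will dose-escalate to 10 mg at Week 2", and minors also take 5 mg until Week 2. Patients may later be held at 5 mg or reduced to it. Those restarting after an ALT/AST interruption "should start at the 5 mg dose level and dose titrate according to Section 7.3.2" (Section 9.1.2).

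**The concern.** Step 2 is mandatory and has a day limit, so it needs a start day. Step 1 supplies that day for patients on 10, 20 or 30 mg and withholds it from patients on 5 mg. Followed literally, the stop never falls due at the dose on which every patient begins. Sites would have to infer a start and could choose different ones.

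The rule exists for the case in which laboratory results are missing, and that is when the laboratory-driven safeguards cannot act. The ALT/AST criteria (Sections 8.5 and 9.1.2), the BNP-doubling trigger (9.1.1) and the closer follow-up at low eGFR (9.1.9) all need a result. Section 9.1.2 expects nearly all drug-related aminotransferase elevations to be asymptomatic. Section 5.1.2.2 says they begin at once after treatment starts and peak about two to four weeks later. Section 5.1.2.1 places the excess fluid-overload risk in the first three to four weeks.

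Some protections do not depend on labs: daily home weights with stop triggers for the first 8 weeks, telephone contacts through Day 45, and advice to consider postponing enrollment. None is a stopping deadline for missing labs, and they thin out later. After Week 8 weights are weekly, no telephone contacts are scheduled, and a weight trigger leads first to a clinic assessment: "Study medication should not be interrupted until the investigator has completed and documented an assessment of fluid overload".

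**Working it through.** This is a reading of the rule plus day counts; no power or error-rate calculation is involved.

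**Inputs**
- Visit window: target day ± 3 days (Protocol Table 5).
- Step-down limit: 6 days after the window (Appendix 1, Section 5.1).
- Interruption limit: 14 days through Week 12, 28 days beyond (same section).
- Target days: Week 1 = 7, Week 2 = 14, Week 12 = 84, Week 24 = 168, Week 48 = 336 (SAP Table 2).
- Schedule after Week 24: "After the Week 24 visit, subjects will continue to be assessed in person every 24 weeks until the study ends" (Protocol Table 5, footnote b).

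**The rule for a patient on 10 mg or more**

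Latest interruption day = target + 3 + 6 + limit. That is target + 23 through Week 12 and, if the 28-day part uses the same start, target + 37 afterwards. For a missed Week 24, the step-down is due by 168 + 3 + 6 = Day 177 and interruption by 177 + 28 = Day 205.

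**The rule for a patient already on 5 mg**

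The de-escalation date does not exist, so the same formula returns no day. Appendix 1 Section 5.2 and protocol Sections 7.3.2 and 7.3.3 do not give a separate missed-lab limit.

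**What a start date would give at 5 mg**

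Two natural starts are the end of the window (target + 3) and the last day on which a step-down would have been due (target + 3 + 6).

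| Missed visit | Window end | From window end | From window end + 6 | As written |
|---|---|---|---|---|
| Week 1 | 7 + 3 = 10 | 10 + 14 = Day 24 | 16 + 14 = Day 30 | none |
| Week 2 | 14 + 3 = 17 | 17 + 14 = Day 31 | 23 + 14 = Day 37 | none |
| Week 12 | 84 + 3 = 87 | 87 + 14 = Day 101 | 93 + 14 = Day 107 | none |
| Week 24 | 168 + 3 = 171 | 171 + 28 = Day 199 | 177 + 28 = Day 205 | none |

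**How long until the next scheduled labs**
- After a missed Week 1: Day 14, so 14 − 7 = 7 days later.
- After a missed Week 2: Day 28, so 28 − 14 = 14 days later.
- After a missed Week 24: Day 336. This is 336 − 205 = 131 days or 336 − 199 = 137 days past the two candidate deadlines, and 336 − 84 = 252 days (36 weeks) after the Week 12 labs.

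**The case against.** The strongest reply concerns the later visits. Section 5.1 ties both its trigger and its 6-day limit to the visit window, so the 28-day limit could be read as running from that window too. A 5 mg patient missing Week 24 would then be due for interruption at about Day 199. The reading is possible, but the sentence does not state it: the only start it names is the de-escalation date. It also leaves the 14-day part, where that start is explicit, unrepaired.

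Second, the missed labs remain owed. The instruction to make every effort covers 5 mg patients. Appendix 1 Section 1 requires sites to keep in contact with patients, Section 4 allows home or local-laboratory collection, and under Section 15.6 failing to complete the minimum remote procedures is a protocol deviation. All of this stands and makes a long gap less likely. None of it sets a date on which drug must stop, and Appendix 1 Section 6 says a failed visit is neither a ground for discontinuation nor a major deviation.

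Third, the late scenario is narrow. The dosing objective is 20 or 30 mg. Reduction or resumption brings an in-clinic visit with chemistry and BNP (Sections 7.3.2, 7.3.3 and 9.6). A patient reduced from 10 to 5 mg because of the missed visit does have a de-escalation date and is outside the gap. Drug is normally dispensed at visits, so continued dosing would usually require courier shipment, which Appendix 1 Section 3 allows. The documents do not say how many patients remain on 5 mg at Week 24 or later. This limits the expected impact, but the rule is still incomplete.

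Finally, the interruption sentence is not expressly confined to de-escalated patients, so this may be only loose wording. That is probably right about intent. It supports adding the missing start date, because sites that agree on the intent can still count from different days.

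**Conclusion.** The concern holds. This is a drafting gap in a safety rule and not a permission to dose indefinitely: the 5 mg sentence waives only the step-down. As written, though, the interruption date cannot be worked out for a patient kept on 5 mg.

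At Weeks 1 and 2 it matters only if consecutive collections fail by every route. From Week 24 the possible overrun is 131 to 137 days. That figure assumes the patient is already on 5 mg, the 28-day part has no window-based start, no unscheduled labs are drawn, and drug supply continues.

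The gap operates only while the COVID-19 mitigations are in force. The SAP Introduction reports that development was discontinued and that sites were told on 10 May 2023, so few or no patients would be affected now. It should be corrected, with low urgency.

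**What to change.** Give the limit a start that every patient has, for both early and late visits. Suggested wording for Appendix 1, Section 5.1:

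> Study drug must be temporarily interrupted if laboratory samples have not been obtained within 14 days (visits through Week 12) or 28 days (visits beyond Week 12) of the dose de-escalation date or, for patients maintained on 5 mg, of the sixth day after the missed visit's window closes.

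This gives 5 mg the same latest stop date as the higher doses and settles the start of the 28-day limit. A stricter alternative counts from the end of the window for 5 mg patients; the sponsor and medical monitor should choose between the two.

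The cost is one sentence, by amendment or site memo, and an occasional extra blood draw or temporary interruption at 5 mg. No endpoint or analysis changes.

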5.2. Resuming or Dose-escalating IP after Interruptions or Changes

Patients who interrupt study drug due to a positive COVID-19 test may resume study drug without an in-clinic visit, at the investigator's discretion, if COVID-19 symptoms are mild.

When the investigator deems that it is safe for the patient to return to the site for an in-person visit, the investigator should conduct an evaluation to determine whether the patient is still eligible to receive IP and to determine the appropriate dose. This should include a confirmation that the reason for interruption was not a per protocol specified reason and that the patient's circumstances have not changed in a manner that would prohibit administration of the investigational drug (eg, the patient is now taking an excluded medication). Once the investigator determines IP administration is appropriate, dosing may proceed as recommended in the table below.

IP Status	Dosing Recommendation
IP temporarily interrupted for any reason (eg, COVID-19, delays in obtaining safety lab, AEs)	Resume IP at last administered dose
IP dose not escalated as required per COVID-19 mitigation plan	Continue last administered dose; consider escalating dose, if appropriate
IP de-escalated for any reason (eg, due to delays in obtaining safety labs, AEs)	Continue last administered dose; consider escalating dose, if appropriate

If the patient is not at the target dose, dose escalation to a higher dose is permitted. Patients who dose escalate must have a telephone call 1 week after dose escalation and an office in-clinic visit (or unscheduled visit, if necessary) 2 weeks (\pm 3 days) after dose escalation to collect clinical chemistry, BNP, and NT-proBNP. Unscheduled visits due to dose escalation should also include assessments detailed in Section 9.6 of the protocol. Once the target dose has been reached and 2-week follow-up completed, the Schedule of Assessments may be resumed.

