2. COVID-19 INFECTED PATIENTS AND STUDY DRUG USE

If a patient enrolled in the study tests positive for severe acute respiratory syndrome coronavirus 2 (SARS-CoV-2), study drug must be temporarily interrupted. The sponsor must be notified immediately for additional guidance.

Study drug may be resumed when the patient no longer presents an active infection (defined as resolution of symptoms or a negative SARS-CoV-2 test), as assessed by the Investigator and/or the patient's physician(s). If COVID-19 symptoms persist (eg, loss of taste or smell), the patient should be encouraged to repeat SARS-CoV-2 testing to minimize the duration of study drug interruption.

Patients who interrupt study drug due to a positive COVID-19 test may resume study drug without an in-clinic visit, at the investigator's discretion, if COVID-19 symptoms are mild, and if the duration of interruption did not exceed 14 days.

The maximum duration of treatment interruption due to COVID-19 infection must be determined based on the patient's symptoms and the investigator's discretion. Instructions for how to resume study drug (ie, appropriate dose for restarting and appropriate visit schedule) are contained in Section 7.3.3.

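### Protocol Appendix 1 Section 5.2 omits the 14-day limit on restarting study drug without a visit after COVID-19, and does not refer longer interruptions to Section 7.3.3

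*Protocol*

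**What the plan says.** Four places in the protocol govern restarting after an interruption.

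- **Section 7.3.3 (main text).** A patient off drug for 14 consecutive days or more needs the medical monitor's approval to resume. After an extended interruption (more than 14 days is the example given), the site discusses starting dose and visit frequency with the monitor. A call at about 1 week and an office visit at 2 weeks follow resumption.
- **Appendix 1 Section 2 (COVID-19 infection).** After a positive test, "study drug must be temporarily interrupted" and "The sponsor must be notified immediately for additional guidance". A restart without a clinic visit is at the investigator's discretion, "if COVID-19 symptoms are mild, and if the duration of interruption did not exceed 14 days". For dose and visits it points to the main text: "Instructions for how to resume study drug (ie, appropriate dose for restarting and appropriate visit schedule) are contained in Section 7.3.3". It sets no fixed maximum for the interruption.
- **Appendix 1 Section 5.1 (missed assessments).** If laboratory samples stay uncollected for 14 days after de-escalation (visits through Week 12) or 28 days (later visits), drug is held until laboratory values can be evaluated and a restart is judged appropriate. For the restart procedure it cites Section 5.2 only.
- **Appendix 1 Section 5.2 (resuming).** "Patients who interrupt study drug due to a positive COVID-19 test may resume study drug without an in-clinic visit", at the investigator's discretion, with mild symptoms as the only condition. It then describes an in-person evaluation of eligibility and dose, followed by a table. For the row "IP temporarily interrupted for any reason (eg, COVID-19, delays in obtaining safety lab, AEs" the recommendation is "Resume IP at last administered dose". The call and 2-week visit are required for patients whose dose is escalated.

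**The concern.** Two sections of one appendix state the same permission with different conditions, and the section that sites are sent to for restarting has the looser one. The dosing row, read alone, also treats a three-day gap and a two-month gap alike, although Section 7.3.3 says the length of and reason for the interruption should be weighed in deciding how to resume safely.

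What is at stake is patient safety rather than any estimate. The protocol starts patients at 5 mg and titrates. It describes fluid-overload risk concentrated in the first three to four weeks after initiation (Section 5.1.2.1) and aminotransferase rises after initiation or a dose increase (Section 5.1.2.2). It gives no data on re-initiation after a gap, so how far those risks return is unknown. The monitor's approval and the early call and visit are the protocol's safeguards for that uncertainty.

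**Working it through.** The plan has no figure to reproduce. The check is a comparison of the rules, followed by a short day count.

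**Step 1: restart without a visit.** Take a patient with mild COVID-19 who has been off drug for 21 days.

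- Appendix 1 Section 2: 21 > 14, so a restart without a visit is not allowed.
- Appendix 1 Section 5.2: symptoms are mild, so it is allowed at the investigator's discretion.

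This is a direct conflict for any interruption longer than 14 days.

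**Step 2: the other conditions after a long interruption.**

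| Item | Section 7.3.3 | Appendix 1 Section 5.2 |
|---|---|---|
| Approval | Medical monitor, from 14 consecutive days | None stated |
| Starting dose | Discussed with the monitor after an extended interruption | Last dose taken, any duration (a recommendation, after an in-person evaluation) |
| Evaluation | Investigator, with the monitor consulted on dose | Investigator; monitor not named |
| Follow-up | Call at about 1 week and visit at 2 weeks after resuming | Call and visit only after escalation |

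Section 9.6 supports the main text by listing resumption after an extended interruption among the reasons for an unscheduled visit with assessments. The medical monitor is not named in Appendix 1 Section 5.1 or 5.2.

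**Step 3: which section a site is sent to.** COVID-19 holds go from Section 2 to Section 7.3.3. Missed-laboratory holds go from Section 5.1 to Section 5.2, with no mention of Section 7.3.3. Neither 5.1 nor 5.2 caps the length of a missed-laboratory hold.

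**Step 4: when a missed-laboratory hold reaches 14 days.** Inputs for a patient above 5 mg: visit window ±3 days (Schedule of Assessments); de-escalation within 6 days of the window; hold starting 14 or 28 days after de-escalation (Section 5.1); approval threshold 14 days (Section 7.3.3).

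- From de-escalation: 14 + 14 = 28 days through Week 12; 28 + 14 = 42 days for later visits.
- Assuming de-escalation falls between window close (day 3 after the target) and 6 days later (3 + 6 = 9), counted from the target visit day:
  - through Week 12: 3 + 28 = 31 to 9 + 28 = 37 days;
  - later visits: 3 + 42 = 45 to 9 + 42 = 51 days.

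Beyond those points Section 7.3.3 requires monitor approval, and the route from 5.1 to 5.2 does not say so.

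**The case against.** The strongest reply is that, apart from the missing 14-day condition, Section 5.2 is silent rather than contradictory. Section 7.3.3 covers any patient and has no pandemic exception, and the table is headed as a recommendation. A site can obey both texts. This largely stands: for approval, dose and follow-up the defect is a missing cross-reference plus a table row with no limit on duration. It does not rescue the no-visit sentence, which differs outright from Section 2.

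The missed-laboratory route is also less exposed than it looks. Laboratory values are evaluated before the restart, and a patient above 5 mg has already been stepped down one level. Such a patient is normally below target, and any later escalation triggers the call and visit. What remains is the interval before escalation, and patients never re-escalated. On the COVID-19 route, Section 2 requires immediate sponsor notification and points to 7.3.3, so the risk needs a site to read 5.2 without the section that created the hold.

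Two stronger readings are tempting and are not supported:

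- A reader might infer that 5.2 allows a restart at the previous full dose, without a visit, after a long gap. That joins the no-visit sentence to the table, but the table follows the in-person evaluation.
- A reader might infer that the appendix overrides 7.3.3 during the pandemic. Nothing says so, and Section 2 of the same appendix relies on 7.3.3.

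Two side issues are clarifications only. Read literally, the Section 5.2 check that the hold was not for a protocol-specified reason would exclude the holds its own row names. The sensible reading is that it screens out protocol safety stops. Aminotransferase holds remain under Section 9.1.2, which restarts them at 5 mg, even though the row lists adverse events.

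**Conclusion.** The point holds. Appendix 1 Section 5.2 is wrong as written on the no-visit restart, because it permits after more than 14 days what Section 2 does not. It is also incomplete for longer interruptions of any cause: its table sets no limit on duration and neither 5.1 nor 5.2 refers to Section 7.3.3, which still governs approval, starting dose and follow-up.

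The size is modest. The documents do not say how many patients restarted after 14 days or more, and no endpoint or analysis is shown to be affected. The 31 to 37 and 45 to 51 day ranges apply to patients above 5 mg and rest on the assumed timing of de-escalation. SAP Section 2 gives 10 May 2023 as the date on which sites were told of the decision to stop development, and calls it the study drug termination date. Taking dosing as ended, the remaining value is a clear rule for judging past restarts, since Protocol Section 15.6 has deviations evaluated and discussed in the final report.

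**What to change.** - **Section 5.2, no-visit sentence:** add the Section 2 condition, so that the permission applies only when the interruption lasted no more than 14 days.
- **Section 5.2, first table row:** limit the last-dose recommendation to interruptions under 14 days. State that Section 7.3.3 governs medical monitor approval, starting dose and follow-up for longer ones.
- **Section 5.1:** add Section 7.3.3 to the cross-reference for restarting.
- **Optional:** reword the check on protocol-specified reasons so that it does not exclude the COVID-19 and missed-laboratory holds, and note that aminotransferase holds restart under Section 9.1.2.

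The cost is protocol wording in two appendix sections. No new visits arise, because Sections 7.3.3 and 9.6 already require the follow-up after an extended interruption.
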